6.1 Primary Objective

- To analyze the association between AKI with RRT and intra-hospital postoperative mortality in cardiac surgery patients compared with AKI patients without RRT

6.2 Secondary Objectives

- To analyze the risk of intra-hospital post-surgical mortality in cardiac surgery patients who complicated with CSA AKI
- To compare the risk of intra-hospital post-surgical mortality in cardiac surgery patients who complicated with CSA AKI with requirement of RRT and without RRT
- To Identify and analyze perioperative factors that play an important role in the incidence of mortality in AKI patients after cardiac surgery

7 Research Methods

7.1 Study Design

This research is a non-experimental study with a retrospective cohort analysis design. Data were secondary collected from patient's registry.

The dependent variable is intra-hospital post-surgical mortality, while the independent variables are cardiac surgery patients with complication of Acute Kidney Injury (AKI) and Renal Replacement Therapy (RRT).

[figure not shown]
Analysis was carried out to determine the relationship between these variables.

7.1.1 Design Overview

This retrospective study was conducted at a tertiary hospital after obtaining approval from the hospital's institutional review board. Data were secondary collected from patient's registry. There is no direct observation or prospective observation to patients.

The need for informed consent was waived since the data analysis was performed retrospectively using hospital electronic medical records (EMR). The diagram below summarizes the study plan (see [Figure 7.1](#)).

Figure 7.1 Study Overview

7.2 Setting

This study will be conducted in tertiary cardiac center in Jakarta, Indonesia. Study began after approval from the ethics committee of Hospital until data collection was completed.

7.2.1 Study Population

Target population for this study is patient aged at least 18 years, who experienced cardiac surgery at adult cardiac surgical unit at tertiary cardiac center from January 2020 to December 2022.

The study population will be identified according to the below inclusion and exclusion criteria.

Inclusion Criteria:

The patient can be included in the study when:

- Data on patients who are at least 18 years old, who experienced cardiac surgery at our tertiary cardiac center from January 2020 to December 2022.

- Data on post-cardiac surgery patients who complicated with Acute Kidney Injury (AKI) which was characterized by an increase in serum creatinine $> 0.3 \text{ mg/dL}$ or $> 150\%$ of the pre-operative serum creatinine level, which was checked within 12 hours post-surgery.
- Data is available in the medical records unit of the Harapan Kita National Heart Center.

Exclusion Criteria:

The patient cannot be included when the patient

- Patients with a previous history of dialysis.
- Data on patients who underwent surgery outside the specified period

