7.3 Variables

The data collected from EMR included demographic data (age, weight, height, sex), type of surgery, comorbidities (history of diabetes, hypertension, stroke, smoking, renal disease), creatinine level, duration of mechanical ventilation, and ICU length of stay. Clinical variables are obtained that included mechanical ventilation time, ICU length of stay, postoperative diuretic, inotropes, vasopressor therapy, postoperative use of intra-aortic balloon pump (IABP), postoperative RRT, and in-hospital mortality. For the study's purpose, several continuous variables are categorized qualitatively such as mechanical ventilation (>48 hours as a cutoff point), ICU (≥ 5 days), postoperative diuretic therapy (yes/no), inotropes and vasopressor therapy ≥ 2 drugs (yes/no), and postoperative use of IABP (yes/no).

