7.3.1 Variables Operational Definition

Table 7.1 Dependent Variable

No.	Variable	Definition	Measured with	Scoring	Scale
1	In-hospital mortality	Patient dies in hospital during treatment after cardiac surgery (patient has never gone home or been discharged from hospital)	Medical record	0 = Not Died 1 = Died	Categorical

Table 7.2 Independent Variables

No.	Variable	Definition	Measured with	Scoring	Scale
1	Acute Kidney Injury	Patients with an increase in serum creatinine more than 1.5 times or > 0.3 mg/dL with urine output < 0.5 cc/kg/hour for 6 consecutive hours.	Medical record	0 = No AKI 1 = With AKI	Categorical
2	Renal Replacement Therapy	Use of a renal replacement therapy machine, either continuous (CVVH) or intermittent (HD), during the period the patient is treated post-operatively until discharge from the hospital.	Medical record	0=Not required 1=Required	Categorical
3	Age	calculated from the day of birth to the day the surgery was performed in years	Medical record	0 = ≤ 60 years 1 = > 60 years	Categorical

		These are surgical procedures undertaken by patients, divided into 5 categories:		
4	Type of valve surgery	1. Coronary Artery Bypass Graft (CABG) is a coronary heart bypass surgery	1 = CABG	
		2. Valves or heart valve surgery is surgery performed on heart valves	2 = Valves	
		3. Mixed valves are heart valve surgery performed simultaneously with other heart surgical procedures (for example coronary or vascular)	3=Mixed Valves	Categorical
		4. Congenital is surgery for congenital heart defects suffered by the patient	4= Congenital	
		5. Other is for surgery that is not included in the 4 categories above (for example Vascular)	5 = Others	
5	Diabetes Mellitus	Obtained from the history of the disease suffered and blood sugar laboratory results.	Medical record	0= No 1= Yes
6	Hypertension	Obtained from the history of the disease suffered by the patient/which was diagnosed	Medical record	0= No 1= Yes

		before undergoing surgery, where the increase in systolic blood pressure is above the normal limit, namely more than 140 mmHg and diastolic blood pressure is more than 90 mmHg.			
7	Serum Creatinine	Serum creatinine value > 3.0 obtained last before surgery, in mg/dL	Medical record	0= No 1= Yes	Categorical
8	History of Stroke	History of stroke diagnoses that the patient has experienced, either with or without sequelae	Medical record	0= No 1= Yes	Categorical

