7.5 Study Size

The sample size was determined based on time, namely all data on adult heart surgery patients between January 1, 2020 - December 31, 2022, who were selected based on acceptance criteria.

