7.7.2 Statistical Methods

The statistical analyses described in this section will be performed as further outlined in the SAP, which will be finalized prior to database lock and will be included in the clinical study report for this protocol. The final SAP will take into account any amendment to the protocol.

General Statistical Methodology:

Descriptive statistics (mean, SD, median, interquartile range) will be provided for continuous variables according to the results of data normality tests. Frequencies and percentages will be presented for categorical and ordinal variables.

All analyzes will consider the security of the dataset.

Primary Outcome Analysis:

The primary outcome in this study is to look at the incidence of death in the treatment of patients who have kidney problems with CRRT or not.

Bivariate analysis was carried out using the chi square/fisher's exact test to see whether there was a difference in the incidence of death in treatment between groups (CRRT vs Non-CRRT)

which was then continued to the multivariate analysis stage if it had a p value <0.25 , multivariate analysis was carried out using regression multiple logistics with a significance level of 0.05 which shows that it is a variable that influences the incidence of death in care.

Secondary Endpoint Analysis:

The secondary outcome in this study is to look at the factors causing CRRT in patients undergoing cardiac surgery with AKI.

Bivariate analysis was carried out using the chi square/ Fisher's exact test to see whether there were differences in patient characteristics between patients who were given CRRT and those who were not, which was then continued to the multivariate analysis stage if it had a p value <0.25 . Multivariate analysis was carried out using multiple logistic regression with The significance level is 0.05 which shows that it is a variable that influences the incidence of CRRT use.

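### Three years of surgery (2020 to 2022) are pooled, but year of surgery is not a candidate in any model, so period confounding of the RRT odds ratio can be neither seen nor removed

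*Combined protocol and SAP*

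**What the plan says.** Section 7.2.1 sets the target population as adults "who experienced cardiac surgery at adult cardiac surgical unit at tertiary cardiac center from January 2020 to December 2022" and excludes "Data on patients who underwent surgery outside the specified period". Section 7.5 makes the same window the only basis for the study size: "The sample size was determined based on time, namely all data on adult heart surgery patients between January 1, 2020 - December 31, 2022". No number of patients or deaths is given.

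The surgery date is used again in Table 7.2, where age is "calculated from the day of birth to the day the surgery was performed in years". The date is not itself named as a data item. Section 7.3 opens its list with "The data collected from EMR included demographic data (age, weight, height, sex), type of surgery" and goes on to comorbidities, creatinine, ventilation, ICU stay, postoperative treatments, RRT and death. None of the 15 independent variables in Table 7.2 is a date, year or period.

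Section 7.7.2 tests for a "difference in the incidence of death in treatment between groups (CRRT vs Non-CRRT") by chi-square or Fisher's exact test, "which was then continued to the multivariate analysis stage if it had a p value <0.25". The multivariable step is "regression multiple logistics with a significance level of 0.05". The secondary analysis of CRRT use follows the same two steps. No analysis by period is planned, and the limitations in Section 7.8 do not mention calendar time.

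**The concern.** The primary result is an association from a non-randomised retrospective cohort. Whether a patient receives RRT can depend on local practice and capacity as well as on the patient's condition, and the plan neither assumes nor checks that these were stable over 36 months. Year of surgery is fixed before AKI, RRT and death, so it cannot be a consequence of RRT and is safe to adjust for in that respect.

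If the RRT share and the underlying mortality rise or fall together over the three years, RRT patients come disproportionately from the high-mortality years and the pooled odds ratio is too high. If the two move in opposite directions, it is too low. Because year is never a candidate, the p < 0.25 screen cannot bring it in. Because nothing is tabulated by year, a reader of the report could not tell whether a period effect is part of the estimate.

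**Working it through.** The plan states no sample size, event count or expected odds ratio, so there is no figure of its own to reproduce. The check is whether the mechanism works and how large it could be.

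**Inputs.** From the documents: three calendar years (Section 7.2.1), and an RRT share of 1 to 10% of AKI patients (Section 4, Abstract). Assumed: equal numbers per year, one common within-year odds ratio, and the yearly RRT shares and non-RRT mortalities shown below.

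**Formula.** For year *i*, let *r* be the RRT share, *m* the mortality without RRT and *m′* the mortality with RRT, where *m′*/(1−*m′*) = OR × *m*/(1−*m*). Sum over years:

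- *a* = Σ *r m′* (RRT, died)
- *b* = Σ *r*(1−*m′*) (RRT, survived)
- *c* = Σ (1−*r*) *m* (no RRT, died)
- *d* = Σ (1−*r*)(1−*m*) (no RRT, survived)

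The pooled odds ratio is *ad*/(*bc*).

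**Worked case, no true association (OR = 1, so *m′* = *m*).** RRT share 3/5/10%, mortality 5/8/15%:

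- *a* = 0.0015 + 0.0040 + 0.0150 = 0.0205
- *b* = 0.18 − 0.0205 = 0.1595
- *c* = 0.0485 + 0.0760 + 0.1350 = 0.2595
- *d* = 2.82 − 0.2595 = 2.5605
- Pooled OR = (0.0205 × 2.5605)/(0.1595 × 0.2595) = 1.27

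**All scenarios.**

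| Assumed drift | RRT share by year | Non-RRT mortality by year | Pooled OR, true OR 1 | Pooled OR, true OR 8 |
|---|---|---|---|---|
| Mild, same direction | 4/5/6% | 7/8/9% | 1.02 | 8.12 |
| Large, same direction | 3/5/8% | 6/8/12% | 1.13 | 8.77 |
| Larger, same direction | 3/5/10% | 5/8/15% | 1.27 | 9.43 |
| Large, opposite directions | 10/5/3% | 5/8/15% | 0.78 | 5.78 |
| RRT share constant | 6/6/6% | 5/8/15% | 1.00 | 7.35 |

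An outer case, with the RRT share falling across the documents' full range (10/5.5/1%) and mortality falling 20/12.5/5%, gives 1.42 at a true OR of 1. Reversing the RRT trend gives 0.63.

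**Reading the table.** At a true OR of 1 the departure from 1 is pure confounding, and it vanishes when only one of the two quantities drifts. At a true OR of 8 this is not so. In the last row the RRT share is constant, so there is no confounding by year, yet the pooled value is 7.35. That gap is non-collapsibility: an odds ratio changes when strata of differing risk are merged, even without confounding. The figures at OR 8 mix the two effects, so the OR 1 column is the one to use for the size of the confounding.

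**The case against.** The strongest reply is that this point could be made of almost any multi-year cohort. The documents give no yearly RRT share or mortality and describe no change of practice. A reader might infer that drift must have occurred because these were pandemic years. The documents do not mention the pandemic, and the point does not rest on it.

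A reader might also infer that any joint drift biases the planned estimate, or that year, because it comes first, can only be a confounder. Neither follows. The final model may contain age, surgery type, pre-operative creatinine, renal history, IABP and vasoactive drugs, and these carry part of any change in case mix. Only drift that the fitted covariates miss confounds the adjusted odds ratio, whereas the figures above are crude. Year may also affect RRT use alone or mortality alone, in which case it does not confound; adjusting for a variable that affects RRT use alone removes no bias and may amplify what remains from other sources. If year modifies the RRT association, a main-effect term does not address that.

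Finally, mild drift moves the odds ratio by about 2%, and with no event count given, each extra parameter has a cost that cannot yet be judged.

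These arguments limit the size and certainty of the problem but leave the omission in place. Age is cut at 60 years, surgery type has five groups, and either may be dropped at the p < 0.25 step, so covariate capture cannot be taken for granted. A later SAP cannot be assumed to fill the gap, because Section 7.7 says that the analysis plans are fully documented in this document.

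**Conclusion.** The point holds as a conditional gap. Calendar time must be known for each patient and appears in no model, so confounding by period would be neither detected nor removed. Availability of the surgery date is an inference from the eligibility rule and the age definition; the date is not a listed field.

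With no true association, the crude pooled odds ratio would be 1.02 under mild drift, 1.13 to 1.27 under large same-direction drift and 0.78 under large opposite drift. These values rest on assumed yearly rates and equal yearly numbers, with no other covariates in the model. They do not show that the study's estimate is biased, and the values at a true odds ratio of 8 should not be read as pure confounding. Priority is minor to moderate: the effect is small unless both drifts are large, but the remedy is cheap.

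**What to change.** 1. Record the surgery date as a data item and add year of surgery (2020, 2021, 2022) to Table 7.2.
2. Include it in the RRT-mortality logistic model regardless of its bivariate p value. If deaths are few, use one linear term for months since 1 January 2020.
3. Report the RRT odds ratio with and without the time term. A difference between the two may partly reflect non-collapsibility, so interpret it alongside item 4.
4. Tabulate RRT share and in-hospital mortality by year. This shows directly whether both changed.

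The cost is one derived field, one or two extra parameters, and a slightly wider confidence interval if there is no time trend. No new data are needed beyond a date that already has to be looked up. Section 7.7.2 provides for a SAP finalised before database lock that takes amendments into account, so the change can be made there.

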7.3 Variables

The data collected from EMR included demographic data (age, weight, height, sex), type of surgery, comorbidities (history of diabetes, hypertension, stroke, smoking, renal disease), creatinine level, duration of mechanical ventilation, and ICU length of stay. Clinical variables are obtained that included mechanical ventilation time, ICU length of stay, postoperative diuretic, inotropes, vasopressor therapy, postoperative use of intra-aortic balloon pump (IABP), postoperative RRT, and in-hospital mortality. For the study's purpose, several continuous variables are categorized qualitatively such as mechanical ventilation (>48 hours as a cutoff point), ICU (≥ 5 days), postoperative diuretic therapy (yes/no), inotropes and vasopressor therapy ≥ 2 drugs (yes/no), and postoperative use of IABP (yes/no).

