[name], MD	Address: [name] [contact] [name] Email : [contact]

Contributing Investigators

1. [name] MD Address:Department of Perioperative Intensive Care and Non-Surgical Anaesthesia
[name]
ORCID ID : [name]
2. [name] MD. Address:Department of Perioperative Intensive Care and Non-Surgical Anaesthesia
[name]
ORCID ID : [name]
3. [name] MD Address:Department of Perioperative Intensive Care and Non-Surgical Anaesthesia
[name]
ORCID ID : [name]
4. [name] MD Address:Department of Perioperative Intensive Care and Non-Surgical Anaesthesia
[name]
ORCID ID : [name]

4 Abstract

The prevalence of acute kidney injury (AKI) varies up to 30% in post-cardiac surgery patients. Of the patients who suffer from AKI, around 1 - 10% will require renal replacement therapy (RRT). Cardiac surgery associated-AKI patients who require renal replacement therapy/dialysis have higher risk of mortality. The purpose of this study was to assess the risk of AKI-RRT on intrahospital mortality, and other factors that have an association with postoperative mortality. The method was non-experimental research design as retrospective cohort analysis. Dependent variable, in-hospital mortality was determined first and then the independent variables were examined to see the relationship between the variables.

Keywords: Acute Kidney Injury (AKI), Renal Replacement Therapy (RRT), cardiac surgery, intrahospital mortality

5 Rational and Background

The overall incidence of mortality post-cardiac surgery in some literatures varies between 2-8%. Cardiac surgery associated - acute kidney injury (CSA-AKI), a common postoperative complication, has increased risk for post-operative mortality. The incidence of mortality in patients complicated with CSA-AKI is up to 60%. The most severe stage of CSA-AKI, which requires dialysis therapy, is an independent risk factor. The prevalence of acute kidney injury is ranged up to 28% in cardiac surgery patients, of which around 1 – 10% of those patients required renal replacement therapy (RRT).¹⁻⁵

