The term of Acute Kidney Injury was developed by the Kidney Disease Improving Global Outcomes (KDIGO) organization in 2012, which is defined it as a sudden decrease (≤ 24 hours) in renal function characterized by an increase in serum creatinine (≥ 0.3 mg/dL or $\geq 50\%$ [1.5 times baseline]), or reduction in urine output <0.5 mL/kg/hour for >6 consecutive hours. Based on these criteria, AKI stage 3 is categorized as acute renal failure or ARF.^{1, 6, 7}

In a study conducted by Bove *et al.* in 2018, AKI is a serious complication after cardiac surgery that increases the incidence of morbidity and mortality. Renal replacement therapy (RRT) has been used as one of the important therapies in patients with severe AKI. Although the incidence of CSA-AKI requiring RRT is reported in about 1-10% of all AKI events after cardiac surgery, it is also shown that patients with severe AKI who require RRT therapy suffer a higher post-operative mortality rate. Previous studies reported intra-hospital mortality up to 43.5% in patients with AKI-RRT. Recent research found that from 412 CSA AKI-RRT patients, 174 patients (42.2%) died intra-hospital, with a EuroScore > 7 , intraoperative bleeding > 1 liter and mechanical ventilation time > 70 hours as other independent risk factors. Meanwhile, post-operative use of furosemide was considered as protective factor in this study (OR 0.48). This information is similar with the results of our previous study regarding the use of diuretics for CSA-AKI patients.⁸⁻¹¹

Considering the significant impact of AKI on the outcomes of patients' post-cardiac surgery, this study aimed to conduct an analysis of the risk factors that contribute to the incidence of post-operative mortality in patients with CSA-AKI, particularly regarding those cases in stages which required RRT. Based on the above background, this study's primary purposes was to analyze association between patients with CSA-AKI with RRT and in-hospital postoperative mortality risk compared to patients with CSA-AKI without RRT.

Study Rationale

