7.8 Limitations of the Research Methods

There are some limitations that should be considered in this study. First, due to the retrospective design used, there were some predictors of CSA-AKI that could not be included. Second, there were limitations in the capacity to do crosschecking due to inability to access patients directly, which may lead to confusion and heterogeneity of the dataset. Finally, data only included a single center, which may not reflect the actual demographics of patients and cardiac disease as distinguished from other centers.

However, the difference from real-life observational data, which is more essential to assess and improve clinical practice worldwide and complement randomized controlled trials by providing clinically relevant, real-world data and provide considerable health economic information.

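### The primary RRT comparison has no grade of AKI severity and no operative risk score among its covariates, only partial proxies selected by p-value, so it is open to confounding by indication

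*Combined protocol and SAP*

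**What the plan says.** **Analysis (7.7.2).** "Bivariate analysis was carried out using the chi square/fisher's exact test to see whether there was a difference in the incidence of death" between the RRT and non-RRT groups (the section writes CRRT), "which was then continued to the multivariate analysis stage if it had a p value <0.25". Multiple logistic regression at the 0.05 level follows, and a significant term is read as one that influences death. No adjustment set is fixed in advance.

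**Data (7.3 and Table 7.2).** Section 7.3 collects "demographic data (age, weight, height, sex" (the list closes there), type of surgery, "comorbidities (history of diabetes, hypertension, stroke, smoking, renal disease), creatinine level, duration of mechanical ventilation, and ICU length of stay". It then adds diuretic, inotrope, vasopressor and IABP use after surgery. Besides RRT, Table 7.2 lists these independent variables:
- AKI yes/no
- age above 60, and type of surgery
- diabetes, hypertension, stroke, smoking and renal disease history
- pre-operative creatinine above 3.0
- prolonged ventilation and prolonged ICU stay
- IABP, inotropic/vasoactive drugs and furosemide infusion

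**Who is compared (7.2.1 and 5).** A creatinine rise above 0.3 mg/dL, or above 150% of the pre-operative value, checked within 12 hours of surgery, is enough for entry. Of patients who need dialysis, Section 5 says: "The most severe stage of CSA-AKI, which requires dialysis therapy, is an independent risk factor". The same section reports a cited cohort of 412 AKI-RRT patients in which death was associated "with a EuroScore > 7 , intraoperative bleeding > 1 liter" and with long ventilation.

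**Limitations (7.8).** Because the design is retrospective, "there were some predictors of CSA-AKI that could not be included".

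**The concern.** RRT is given to patients whose kidneys, and often circulation, are failing. Comparing them with all other AKI patients, including those just over the entry threshold, sets the sickest against a mixed group. Unless severity before RRT is in the model, the RRT coefficient carries both any effect of RRT and the prognosis that led to it.

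The background names the severest AKI stage, EuroSCORE and bleeding as risk factors for death, yet none of them is a covariate. The stake is the primary result: a large, significant odds ratio could arise with no RRT effect, and the plan's wording would present it as an influence on mortality.

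**Working it through.** **1. Does any covariate grade AKI severity?** No.
- AKI is coded 0/1, and Section 7.7 restricts all analyses to AKI patients, so the flag is constant and adjusts for nothing. Table 7.2 attaches a urine-output condition that 7.2.1 lacks. On a literal reading the flag could therefore vary, but it would still be a threshold and not a grade.
- Creatinine is a pre-operative flag (above 3.0 mg/dL). It describes baseline renal function and not the postoperative injury.

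**2. Does any covariate measure operative risk or general illness?** Partly.
- Age above 60, type of surgery, diabetes, hypertension, stroke, renal history and pre-operative creatinine carry part of operative risk. EuroSCORE and intraoperative bleeding are absent.
- IABP and inotropic/vasoactive use carry part of postoperative illness. Neither they nor ventilation above 48 hours and prolonged ICU stay have a stated timing relative to RRT, so some may be consequences of RRT or of what followed it.
- On the plan's wording, each enters only if bivariate p < 0.25. Adjustment is neither absent nor assured.
- Sex is collected (7.3) but is not in Table 7.2.

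**3. How large could the distortion be?** The plan gives no effect size, power or number of patients ("The sample size was determined based on time, namely all data on adult heart surgery patients"), so there is no design figure to reproduce. The one figure nearby that can be checked, the cited RRT mortality, agrees: 174/412 = 42.2%.

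For an omitted binary factor that multiplies the risk of death by RR and is present in a share p1 of RRT and p0 of non-RRT patients, with no true RRT effect:

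apparent risk ratio = [p1(RR − 1) + 1] / [p0(RR − 1) + 1]

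All inputs below are assumptions.

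| Omitted factor | p1 | p0 | RR | Apparent risk ratio |
|---|---|---|---|---|
| High operative risk | 0.60 | 0.25 | 2 | 1.60/1.25 = 1.28 |
| High operative risk | 0.60 | 0.25 | 3 | 2.20/1.50 = 1.47 |
| Severe AKI, lowest corner | 0.80 | 0.20 | 3 | 2.6/1.4 = 1.86 |
| Severe AKI | 0.80 | 0.20 | 4 | 3.4/1.6 = 2.12 |
| Severe AKI, highest corner | 1.00 | 0.10 | 5 | 5.0/1.4 = 3.57 |

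The highest corner is an extreme. With every RRT patient severe, the RRT group has no non-severe patients to compare.

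**4. What does this do to the test?** Take the third row and assume 8% mortality without the severity factor. Mortality is then 0.08 × 2.6 = 20.8% with RRT and 0.08 × 1.4 = 11.2% without. The odds ratio, which is what the plan's model reports, is (0.208/0.792)/(0.112/0.888) = 2.08. With an assumed 500 to 1,000 AKI patients and 5% to 10% on RRT (Section 5 gives 1% to 10%), the chance that the unadjusted test gives p < 0.05 is 34% to 75% (two-sided, normal approximation), against a nominal 5%. In a milder case (RR 2, 80% versus 40%) it is 9% to 18%.

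**5. Set against a plausible crude result.** If non-RRT mortality were 5%, 10% or 20% (assumed) and RRT mortality the cited 42.2%, the crude risk ratio would be 8.4, 4.2 or 2.1. Confounding of the size shown could be a material part of that, but need not be all of it.

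**The case against.** **Operative risk and illness are not ignored.** A reader might infer that nothing in the model measures them. Table 7.2 does not support that. Age, surgery type, comorbidities, IABP and inotropic/vasoactive use are all candidates, and two factors from the cited cohort (ventilation time and furosemide) have counterparts there. This stands. The gap is that the proxies are partial, screened by p-value and partly undated, and that none grades kidney injury.

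**The cited factors come from RRT patients only.** They predict death among patients on RRT. That does not show that they differ between RRT and non-RRT patients, as confounding also requires. This stands too, so the shares in the table are assumptions. A plan cannot show that the estimate *is* confounded, only that it is open to confounding.

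**The objective is an association with an RRT requirement.** Read as a severity marker, RRT need not be separated from severity. That is a legitimate question, and it is why both estimates should be shown. It does not cover the plan's adjustment of the RRT term followed by language of influence.

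**Severity data may not be to hand.** It is tempting to say that peak or last pre-RRT creatinine is already collected. Section 7.3 lists only a creatinine level, and neither serial values nor an RRT start time is named. Comparing a pre-RRT value in one group with a whole-stay peak in the other would also measure the covariate differently by group. The early postoperative value avoids this, because eligibility depends on it in everyone.

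**Sex.** Section 7.7.2 does not expressly confine candidates to Table 7.2, so its exclusion is the natural reading and not a stated rule.

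**Conclusion.** The concern holds in this form. The plan offers no AKI severity grade and no operative risk score for its primary comparison, and leaves the partial proxies to a p < 0.25 screen. The RRT association is therefore open to substantial residual confounding by indication. Section 7.8 speaks of missing predictors of AKI, which is a different matter, and the wording of influence goes beyond what the design can carry.

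If there were no true RRT effect, the spurious risk ratio would be about 1.9 to 3.6 from AKI severity and 1.28 to 1.47 from operative risk. These rest wholly on the assumed shares and risk ratios, and treat the omitted factor as not captured by any other covariate. The proxies that do enter would reduce them. This should be changed, but it does not defeat the study: the association can still be reported, with its meaning stated correctly.

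**What to change.** 1. Add sex to Table 7.2 and force sex, age and type of surgery into the primary logistic model whatever their bivariate p.
2. Derive the ratio of the creatinine checked within 12 hours after surgery to the pre-operative value, in the same way in both groups, and flag any patient whose RRT began before that sample. Report the RRT odds ratio with and without this term. Add a sensitivity analysis that limits the comparator to the largest early rises, with the cut-off fixed before outcomes are examined.
3. Where already charted, abstract EuroSCORE II and intraoperative bleeding as pre-exposure covariates.
4. Name confounding by indication in 7.8, and in 7.7.2 replace the language of influence with language of association.

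**Cost.** Sex is already collected, and both creatinine values are needed to establish eligibility. The flag in (2) needs the RRT start time, which 7.3 does not list, and (3) needs a few more fields from the same records. The forced set uses 1 + 1 + 4 = 6 parameters (type of surgery has five categories), which should be weighed against the number of deaths. An early creatinine ratio captures severity only in part, so some confounding will remain. The severity-adjusted estimate also answers a narrower question than RRT as a marker of severity, so both belong in the report.
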